### **6.2 Reported Adverse Events and Potential Risks**

Metformin is considered to have a favorable safety profile in diabetes patients (109). In a US double-blind clinical trial for patients with type 2 diabetes (metformin n=141; placebo n=145), gastrointestinal symptoms such as diarrhea (53.2% vs. 11.7% placebo), nausea and vomiting (25.5% vs. 8.3% placebo), abdominal discomfort (6.4% vs. 4.8% placebo), flatulence (12.1% vs. 5.5% placebo), indigestion (7.1% vs. 4.1% placebo), and asthenia (9.2% vs. 5.5% placebo) were the most common reactions to the drug. These symptoms were dose-dependent,

transient, and resolved spontaneously with continued use (Glucophage® (metformin hydrochloride tablets) label information). Diarrhea led to discontinuation of medication in 6% of subjects treated with metformin hydrochloride. Additional adverse reactions were reported in 1% to 5% of subjects receiving active drug; those more commonly reported than in the placebo group include abnormal stools, hypoglycemia, myalgia, lightheaded, dyspnea, nail disorder, rash, increased sweating, taste disorder, chest discomfort, chills, flu syndrome, flushing and palpitation (Glucophage® (metformin hydrochloride tablets) label information).

A recently published multicenter, randomized, placebo-controlled trial in patients with type 2 diabetes reported on vitamin B12 deficiency with long-term metformin treatment. Compared with placebo, metformin treatment was associated with a mean decrease in vitamin B12 concentration of ~19% (95% confidence interval (CI) –24% to –14%; p<0.001). The absolute risk of vitamin B12 deficiency (<150 pM) at study end was 7.2 percentage points higher in the metformin group than in the placebo group (95% CI 2.3 to 12.1; p=0.004) (110).

According to the package insert, lactic acidosis is a rare, but serious, metabolic complication that can occur due to metformin accumulation during treatment with metformin hydrochloride. When it occurs, it is fatal in approximately 50% of the cases. Lactic acidosis may also occur in association with a number of pathophysiologic conditions, including diabetes mellitus and whenever there is significant tissue hypoperfusion and hypoxemia. Lactic acidosis is characterized by elevated blood lactate levels (>5 mmol/L), decreased blood pH, electrolyte disturbances with an increased anion gap, and an increased lactate/pyruvate ratio. Metformin plasma levels >5 µg/mL are generally found when metformin is implicated as the cause of lactic acidosis.

Reported incidence of lactic acidosis in patients receiving metformin hydrochloride is very low (approximately 0.03 cases/1000 patient-years, with approximately 0.015 fatal cases/1000 patient-years). In more than 20,000 patient-years of exposure to metformin in clinical trials, there were no reports of lactic acidosis. Reported cases have occurred primarily in diabetic patients with significant renal insufficiency, including both intrinsic renal disease and renal hypoperfusion, and in those with multiple concomitant medical/surgical problems and who take multiple concomitant medications. Patients with congestive heart failure require pharmacologic management, in particular those with unstable or acute congestive heart failure who are at risk of hypoperfusion and hypoxemia and increased risk of lactic acidosis (Glucophage® (metformin hydrochloride tablets) label information).

The risk of lactic acidosis increases with the degree of renal dysfunction and patient age. Drug should be withheld in the presence of any condition associated with hypoxemia, dehydration, or sepsis. Because impaired hepatic function can significantly impair the ability to clear lactate, metformin should generally be avoided in patients with clinical or laboratory evidence of hepatic disease. Alcohol can potentiate the effects of metformin hydrochloride on lactate metabolism. Drug treatment should be temporarily discontinued prior to any intravascular radiocontrast study and for any surgical procedure (111). The onset of lactic acidosis is often subtle, and accompanied by nonspecific symptoms such as malaise, myalgia, respiratory distress, increasing somnolence, and nonspecific abdominal distress. There may be associated hypothermia, hypotension, and resistant bradyarrhythmias with more marked acidosis (Glucophage® (metformin hydrochloride tablets) label information).

In support of the previously reported low risk of lactic acidosis, a recently published systematic review assessed the risk with metformin use in type 2 diabetes mellitus. Pooled data from 347 comparative trials and cohort studies revealed no cases of lactic acidosis in 70,490 patient-years of metformin use. The authors concluded that there was no evidence from prospective comparative trials or from observational cohort studies that metformin is associated

with an increased risk of lactic acidosis compared to other antihyperglycemic treatments (112, 113).

Unlike sulfonylureas, metformin does not produce hypoglycemia in either type 2 diabetes patients or normal subjects and does not cause hyperinsulinemia (109).

Carcinogenicity studies have been performed in rats (dosing duration of 104 weeks) and mice (dosing duration of 91 weeks) at doses up to and including 900 mg/kg/day and 1500 mg/kg/day, respectively. Both doses are approximately four times the maximum recommended human daily dose of 2000 mg based on body surface area. No evidence of carcinogenicity was found in either male or female mice or in male rats. There was, however, an increased incidence of benign stromal uterine polyps in female rats at 900 mg/kg/day (109). Metformin was not mutagenic in the Ames, mouse lymphoma, human lymphocyte chromosome aberration, or mouse micronucleus tests (109).

The fertility of male and female rats was unaffected by metformin when administered at doses as high as 600 mg/kg/day, which is approximately three times the recommended human daily dose based on body surface area (109).

### **6.3 Source of Study Agent**

Metformin tablets, 850 mg will be purchased from a commercial source through the University of Arizona Cancer Center (UACC) Research Pharmacy. We will contract with Pharm Ops, Inc (Phillipsburg, NJ) to manufacture a clinical supply of the placebo tablets using inert excipients. Pharm Ops, Inc. has manufactured placebo products for a number of NCI-sponsored chemoprevention trials.

### **6.4 Agent Storage and Distribution**

Metformin and placebo tablets will be stored in the UACC Research Pharmacy at room temperature [20-25°C] and protected from environmental extreme. It will be dispensed to the study staff in light-resistant containers for distribution to the study participants.

### **6.5 Registration/Randomization**

Subjects will be considered registered on the date they sign the approved informed consent document with a member of the study staff. Randomization will be performed using computer-generated random permuted blocks.

### **6.6 Blinding and Unblinding Methods**

To retain the blind, metformin and placebo tablets will not be identified by product names but by a unique randomization number. The randomization number is assigned to the subject upon completion of eligibility evaluation.

A list of randomization numbers linked to active or placebo agent will be generated by the study statistician or the designated data manager and forwarded to the UACC Research Pharmacy. The UACC Research Pharmacy will dispense the study agent to the study staff by randomization number. The study agent bottles will be identified with the subject randomization number but with no product information on the label. The study staff will dispense the product to subjects based on the assigned randomization number. None of the staff interacting with subjects will know the link between randomization number and actual product. The code that identifies the product will be kept by the study statistician or the designated data manager.

Unblinding is not expected to occur until all subjects complete the intervention and data entry is complete. If deemed medically necessary, study agents may be unblinded by the

Principle Investigator in consultation with the Medical Director in the event of a serious adverse event.

**6.8 Agent Disposal**

Unused agents will be returned to the clinic for compliance check and then be disposed according to the UA waste disposal guidelines.

## 7. CLINICAL EVALUATIONS AND PROCEDURES

### 7.1 Schedule of Events

Study Events	Consenting/ Screening	Baseline/ Randomization	Intervention (12 month (52 ± 4 wks))								
			Months 1 - 3	Month 3 Visit (13 ± 2 wks)	Months 4 - 6	Month 6 Visit (26 ± 4 wks)	Months 7 - 9	Month 9 Visit (39 ± 2 wks)	Months 10 - 12	Month 12 Visit (52 ± 4 wks)	Follow up
Consent, med records release form	X										
Medical history, performance status	X										
anthropometric measurements	X	X				X				X	
Vital signs (Temp, BP, Pulse)	X	X		X		X		X		X	
Concomitant meds	X	X		X		X		X		X	
Breast cancer risk assessment	X										
Menstrual pattern/cycle review	X	X		X		X		X		X	
Menstrual cycle diary	X	X	X	X	X	X	X	X	X	X	
Fasting blood (CBC/Diff, CMP, lipids, FSH  , estradiol  )	X									X	
Fasting blood for research endpoints		X				X				X	
Urine pregnancy test	X	X		X		X		X		X	
Urine for research endpoints		X				X				X	
AFFQ, AAFQ		X								X	
NAF collection		X				X				X	
Breast MRI 		X				X				X	
Core biopsy, if consented		X				X					
Final eligibility assessment		X									
Randomization		X									
Dispense study agent		X				X					
Intake calendar			X	X	X	X	X	X	X	X	
Adverse events diary		X	X	X	X	X	X	X	X	X	X
Adverse events review		X		X		X		X		X	X
Return study agent						X				X	
Compliance assessment				X		X		X		X	
Case report form completion	X	X		X		X		X		X	X
Telephone/email contact 			X		X		X		X		

 Study personnel will contact subjects within a week after study agent has been initiated and within a week following scheduled dose increase to assess compliance and any potential problems. Additional periodic telephone or email contact will occur between study visits and as needed to review study procedures, adverse events, concomitant medications, and to address any subject concerns.

 FSH (follicle-stimulating hormone) and/or estradiol at screening for women with uncertain menopausal status.

 Women who cannot fit into the MRI scanner due to the large body size will continue the study and undergo all other study procedures.

## **7.2 Consenting/Screening**

Potential subjects will present to clinic for a detailed discussion of the protocol with the study coordinator. Signed informed consent will be obtained prior to any study-related activities or procedures being conducted. Subjects are registered onto the protocol on the day of consent. Participants will then undergo the following procedures for screening.

- Review of medical history and medication usage history
- Collection of demographic information (age, race/ethnicity).
- Collection of anthropometric measurements (weight (wt), height, waist circumference, waist-hip ratio). Body weight will be measured with participants standing on a calibrated scale with minimal movement with hands by their side and shoes and excess clothing removed. Waist and hip circumference will be measured in a standing position with a flexible tape. Waist circumference will be measured at the midpoint between the lowest rib and the top of the iliac crest on the bare abdomen. Participants will be asked to relax and exhale for the measurement. Hip circumference will be measured at the level of the greatest protrusion of the gluteal muscles, with minimal clothing. Participants will be asked to stand with their weight evenly distributed on both feet and legs slightly parted, making sure not to tense the gluteal muscles. When recording the measurement, the study personnel will ensure that the tape is not too tight or too loose, is lying flat on the skin, and is horizontal.
- Collection of breast cancer risk information (family and personal history of breast cancer, age at menarche, parity, and prior breast biopsy).
- Collection of information on menstrual patterns/cycles.
- Measures of vital signs (temperature, blood pressure and pulse).
- A fasting blood sample for complete blood count with differential (CBC/w diff), comprehensive metabolic panel (CMP), lipids, and follicle-stimulating hormone (FSH) and/or estradiol for women with uncertain menopausal status. The screening blood work may be repeated, if clinically indicated.
- Urine pregnancy test.

## **7.3 Evaluations During Study Intervention**

Participants who meet all selection criteria will undergo the following baseline procedures. When feasible, these procedures will be scheduled in the midluteal phase of the menstrual cycle.

- Anthropometric measurements including wt, waist circumference, waist-hip ratio.
- A fasting blood for research biomarkers.
- Collection of urine for urine pregnancy test and research tests.
- Vital signs.
- Update information on menstrual patterns/cycles.
- Update medication usage.
- Completion of the Arizona Food Frequency Questionnaire (AFFQ) to measure usual dietary intake and the Arizona Activity Frequency Questionnaire (AAFQ) to assess usual physical activity.
- Nipple aspirate fluid, for those who are able to produce NAF, for metabolomic analysis. Breasts will be warmed and massaged. Nipple fluid will be aspirated by a hand-held aspirator.

- MRI assessment of breast density. All MRI images will be acquired on a 3T MRI scanner located in the department of Radiology of the University of Arizona Medical center. Fat-water imaging will be performed using the radial Gradient-Echo and Spin-Echo (GRASE) technique developed by co-investigator, [name] (114). Women who cannot fit into the MRI scanner due to the large body size will continue the study and undergo all other study procedures.
- Optional core needle biopsy. For participants who consent to this optional procedure, the medical specialist will use a 14-gauge needle under the ultrasound guidance to obtain up to 8 tissue cores from one of the breasts.

Following completion of baseline evaluation, participants will be randomized to receive metformin or placebo for 12 months. Participants will receive a supply of study medication. Participants will be asked to take one 850 mg metformin or one placebo tablet daily with a full 8 oz glass of water with a meal for the first four weeks, then two 850 mg metformin or two placebo tablets daily with meals for the remainder of the study. The same starting dose and gradual dose escalation up to 2,000 mg per day is used to minimize gastrointestinal symptoms for glycemic control in diabetics (GLUCOPHAGE® prescribing information).

Participants will be asked to keep an adverse event diary and menstrual calendar throughout the study. In addition, participants will be provided with an intake calendar for recording medication usage. Study personnel will contact study participants within a week after study agent has been initiated and within a week following scheduled dose increase to assess compliance and any potential problems.

Participants will return to the clinic at month 3 ( $13 \pm 2$  wks) to undergo the following procedures:

- Collection of urine for urine pregnancy test.
- Vital signs.
- Update information on menstrual cycles.
- Update medication usage.
- Side effect evaluation.

Participants will return at month 6 ( $26 \pm 4$  wks) to undergo the following procedures:

- Collection of urine for urine pregnancy test and research tests.
- Vital signs.
- Update information on menstrual patterns/cycles.
- Update medication usage.
- Side effect evaluation.
- Return unused pills.
- Receive a new supply of study medication.
- Collection of wt, waist circumference, waist-hip ratio measurements.
- Collection of a fasting blood and NAF sample for research biomarkers.
- MRI assessment of the breast. Women who cannot fit into the MRI scanner due to the large body size will not undergo the MRI assessment.
- Optional breast core biopsy.

When feasible, the month 6 procedures will be scheduled in the midluteal phase of the menstrual cycle.

Participants will return to the clinic at month 9 ( $39 \pm 2$  wks) after initiation of agent intervention to undergo the following procedures:

- Collection of urine for urine pregnancy test.
- Vital signs.
- Update information on menstrual patterns/cycles.
- Update medication usage.
- Side effect evaluation.

Study personnel will contact study participants at least once and as needed between clinic visits to assess compliance and any potential problems.

#### **7.4 Evaluations at Completion of Study Intervention**

At the end of the 12-month agent intervention ( $52 \pm 4$  wks), participants will return to the clinic to undergo the following procedures:

- Collection of urine for urine pregnancy test and research tests.
- Vital signs.
- Update information on menstrual patterns/cycles.
- Update medication usage.
- Return unused drugs.
- Side effects evaluation.
- Anthropometric measurements including wt, waist circumference, waist-hip ratio.
- A fasting blood for CBC/CMP/lipids and research biomarkers.
- NAF collection.
- MRI assessment of breast density. Women who cannot fit into the MRI scanner due to the large body size will not undergo the MRI assessment.
- Completion of AFFQ and AAFQ.

When feasible, the month 12 procedures will be scheduled in the midluteal phase of the menstrual cycle.

Participants will be instructed to take the study agent until the day of the last study procedure.

#### **7.5 Post-intervention Follow-up Period**

Following the study intervention, participants will be followed for 2 weeks for any adverse reactions.

### **8. SPECIMEN MANAGEMENT**

#### **8.1 Collection and Handling Procedures**

##### **Blood Samples**

##### Clinical labs

Fasting blood samples will be collected during screening and at the end of intervention for CBC with differentials, and CMP/lipids. FSH and/or estradiol will be done at screening for women with unknown menopausal status. Approximately 15 ml of blood will be drawn to one 3-5 ml EDTA and one 7-10 ml SST or tiger top Vacutainer tubes as directed by the clinical lab, and labeled with the subject name. Samples will be processed and stored according the standard

protocol for each. The serum tube (SST or tiger top for CMP) will be allowed to clot for approximately 30 minutes at room temperature then centrifuged within 1 hour of collection for serum separation. The EDTA tube (for CBC/diff) will be gently inverted to mix for anticoagulation. All samples will be stored under refrigeration prior to transfer to the commercial laboratory facility on the same day as obtained with a completed lab requisition.

#### Research biomarkers

Fasting blood samples will also be collected during baseline, month 6 and at the end of intervention for research biomarker analyses. Approximately 30 ml of fasting blood will be drawn into two 10 ml SST or tiger top Vacutainer tubes and one 10 ml heparin Vacutainer tube. The blood in the SST or tiger top tubes will be allowed to clot for approximately 30 minutes at room temperature then centrifuged for serum separation. The heparin tube will be gently inverted to mix for anticoagulation. Serum from the SST tubes will be aliquoted into 10 x 1-2 ml cryovials and plasma from the heparin tube will be aliquoted into 5 x 1-2 ml cryovials. Samples will be labeled with the study ID, subject ID, and date of collection and stored at -80°C until analyses.

NAF will be collected at baseline, month 6 and at the end of intervention. NAF will be collected in small capillary tubes. The capillary tubes will then be stored in a 5 ml cryotube. Cryotubes will be labeled with the study ID, subject ID, and date of collection and stored at -80°C until analyses.

Clean catch urine will be collected at baseline, month 6 and at the end of intervention. Urine will be aliquoted into 4 x 1-2 ml cryovials. Cryovials will be labeled with the study ID, subject ID, and date of collection and stored at -80°C until analyses.

#### Breast Biopsies

Optional breast biopsies will be performed at baseline and month 6. Up to eight tissue cores will be collected at each procedure. Half of the tissue will be immediately fixed in 10% neutral buffered formalin for 24 hours, and then transferred to 70% ethanol prior to routine processing and paraffin embedding (FFPE). Representative FFPE specimens will be reviewed by UAMC pathology department. The remaining half will be placed in cryogenic vials or bags and flash frozen in liquid nitrogen and then stored at -80°C for future studies. Samples will be labeled with the study ID, subject ID, and date of collection.

### **8.3 Tissue Banking**

Biological specimens collected for this study that are not expended in analyses described in this protocol may be retained ("banked") for future research testing only with the

consent of the subject. With that consent, remaining serum/plasma and frozen tissue will be stored at  $-80^{\circ}\text{C}$  for future testing; paraffin embedded tissue will be stored in locked cabinets at room temperature. A log will be kept for all stored specimens regarding the date of collection, subsection identification number, study number, and the storage location.

## 9. STATISTICAL CONSIDERATIONS

### 9.1 Analysis Plan

The primary study endpoint is to compare the change in breast density as measured by FWR-MRI (when measured at baseline, 6 and 12 months) between metformin and placebo groups. Additional endpoints such as systemic hormone and cytokines, body weight, waist circumference, and waist-hip ratio will be measured at baseline, 6 and 12 months. Analysis for all study endpoints will be based on a linear mixed-effects model for the observed values across time, to adjust for the correlation among measurements within the same woman. The main effects in the model will be time (0, 6, 12), treatment group (metformin versus placebo), and the interaction between time and treatment group. The time parameter tests if there is a change among placebo treated women, while the group-by-time interaction tests if the change in metformin treated women differs from that in the placebo group. We expect that a simpler covariance structure, such as compound symmetry, will be adequate for repeated measurements within the same woman (since the measurements are equally spaced). Alternatively, we will compare correlation structures for the longitudinal measurements using Akaike's information criterion. All endpoints will be first assessed for normality, and transformations (such as a logarithmic transformation) will be used as necessary to reduce skewness prior to statistical analysis.

Secondary analyses will assess whether differences in the changes in FWR-MRI between the metformin and placebo groups remain after adjustment for potential explanatory variables, such as changes in body weight, systemic hormones, and cytokines. These explanatory variables will be added as independent predictors in the linear mixed-effects models. These analyses will be restricted to explanatory variables that have demonstrated statistically significant metformin effects across time.

For the metabolomic aim, pre- to post-intervention changes in all detectable compounds of known identity (currently comprising 397 biochemicals using the standard platforms offered by Metabolon, Inc) will be determined and compared between treatment groups using a two-sample t-test. An estimate of the false discovery rate ( $q$ -value) will be calculated (115) to take into account the multiple comparisons that normally occur in metabolomic-based studies. A low  $q$ -value ( $q \leq 0.10$ ) is an indication of high confidence in a result. While a higher  $q$ -value indicates diminished confidence, it does not necessarily rule out the significance of a result. Other lines of evidence may be taken into consideration when determining whether a result merits further scrutiny. Such evidence may include a) significance in another dimension of the study, b) inclusion in a common pathway with a highly significant compound, or c) residing in a similar functional biochemical family with other significant compounds.

Exploratory analyses will assess whether the observed metformin-induced changes in metabolite features are correlated with changes in FWR-MRI, body weight/composition, systemic hormones, and cytokines. The correlation will be estimated using a Pearson correlation coefficient. It is expected that any changes in these variables in the placebo group will reflect random variation only. Thus, these analyses will be restricted to the metformin group to overcome dilution of the potential correlations by individuals in the placebo group.

Exploratory analyses also will explore the correlation between baseline metabolite features and FWR-MRI, systemic hormones, and cytokines. These analyses will be restricted to

the metabolite features that are members of a common pathway to reduce the potential for an inflated alpha level.

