### **9.2 Sample Size Justification**

Our sample size ensures adequate power to test all primary specific aims. We assume an initial sample size of 75 women per arm and allow the possibility of up to 20% dropout for the 12-month follow-up measurement. This results in at least 60 evaluable women per group. To justify the sample size, we use the simplified comparison of change between 12 months versus baseline (ignoring the 6 month measurement). For the FWR-MRI-derived change in breast density, we will be able to detect a decrease of 0.516 standard deviation (SD) units in the metformin treated women with 80% statistical power, assuming a two-sided  $\alpha$  of 0.05. To estimate what this change would be in relation to breast density, we used the relationship between breast density and  $\log(\text{Fra50})$  based on our previous data. Based on an analysis of our cross-sectional data, the estimated SD of  $\log(\text{Fra50})$  is 2.40. Thus, a decrease of 0.516 SD units corresponds to a change of  $-1.2384$  ( $-0.516 \times 2.40$ ). Based on the regression line, this is equivalent to a 10% decrease in breast density as determined by standard mammography. For the additional primary outcomes (such as systemic hormones, cytokines, and weight), we will be able to detect a difference of 0.516 SD units with 80% statistical power, assuming a sample size of 60 evaluable women per group. Based on our previous experience, we anticipate that 65% of the proposed cohort will provide sufficient NAF for metabolomic analysis, which results in 39 women per group (allowing for up to 20% drop-out). This will allow us to detect a difference of 0.643 SD units with 80% statistical power.

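### The planned models use the pre-randomisation baseline inefficiently: a common baseline mean and ANCOVA would cut variance by (1−ρ)/2 with complete data, from 35% at ρ = 0.3 to 5% at ρ = 0.9

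*Combined protocol and SAP*

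**What the plan says.** Section 9.1 fits a linear mixed model to the observed values at baseline, 6 and 12 months for breast density, hormones, cytokines and anthropometric measures. "The main effects in the model will be time (0, 6, 12), treatment group (metformin versus placebo), and the interaction between time and treatment group". It describes the time parameter as the change in placebo women, "while the group-by-time interaction tests if the change in metformin treated women differs from that in the placebo group". On covariance: "We expect that a simpler covariance structure, such as compound symmetry, will be adequate for repeated measurements within the same woman", with a comparison of structures by AIC as the alternative.

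For metabolomics, the same section takes "pre- to post-intervention changes in all detectable compounds of known identity", to be "compared between treatment groups using a two-sample t-test".

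On timing, Section 7.3 says: "Following completion of baseline evaluation, participants will be randomized to receive metformin or placebo for 12 months". Section 3 gives the same order.

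For power, Section 9.2 says "we use the simplified comparison of change between 12 months versus baseline (ignoring the 6 month measurement"). It quotes detectable differences of 0.516 SD with 60 women per arm and 0.643 SD with 39 per arm (NAF), both at 80% power.

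Section 9 has no baseline covariate and no common-baseline constraint. The only covariates it adds are explanatory variables such as changes in weight, hormones and cytokines, in secondary analyses.

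**The concern.** With baseline as a modelled response and a free treatment main effect, the model estimates a separate baseline mean for each arm. With visit as a three-level factor and complete data, the month-12 interaction estimate is then the difference in mean change from baseline. Because baseline precedes randomisation, the true baseline difference between arms is zero. Subtracting its whole observed value over-corrects whenever baseline and follow-up are imperfectly correlated. The metabolite t-test on change does the same.

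At stake is precision. The trial is sized at 80% power with exactly 60 evaluable women per arm, or 39 for NAF. Women who cannot fit the scanner stay in the study without MRI (Section 3), so the number with MRI could fall below 60 if attrition reaches the planned 20%. A model change that needs no further women is worth having.

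**Working it through.** **Inputs.** From Section 9.2: 75 per arm randomised, 20% dropout, 60 per arm evaluable, 39 per arm with NAF, two-sided α 0.05, 80% power, cross-sectional SD of log(Fra50) 2.40. Assumed, because the documents do not give it: ρ, the within-woman correlation between baseline and month 12, taken from 0.3 to 0.9. Equal variances at baseline and follow-up are also assumed.

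**The plan's own figures.** 75 × 0.8 = 60 and 60 × 0.65 = 39. The noncentral t gives 80.0% power at 0.516 SD with 60 per arm, and 80.0% at 0.643 SD with 39 per arm. Both reproduce.

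**Variance comparison at month 12.** For n per arm and outcome variance σ²:

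- Difference in mean change: (2σ²/n) × 2(1−ρ).
- Baseline-adjusted difference (ANCOVA or common baseline mean): (2σ²/n) × (1−ρ²).
- Ratio, adjusted to planned: (1−ρ²) / [2(1−ρ)] = (1+ρ)/2, a reduction of (1−ρ)/2.

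Generalised least squares for the three-visit model, with free and then common baseline means, gives the same complete-data ratios: 0.65, 0.75, 0.85 and 0.95.

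**Dropout.** With 75 per arm, 20% missing at month 12, compound symmetry and all observed data used, the ratios are 0.697, 0.786, 0.873 and 0.958.

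**Cost of estimating the slope.** Estimating the baseline slope inflates the adjusted variance by 1 + 1/(2n−4): 1.0086 at n = 60 and 1.0135 at n = 39. The gain is cancelled where (1+ρ)/2 times that factor equals 1, that is, at ρ = 0.983 and 0.973.

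**Results.** Detectable differences are in SDs of change at 80% power, and power is at the plan's 0.516 SD. The last three columns include the slope cost and assume complete data.

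| ρ | Variance cut, complete data | Variance cut, 20% missing | Detectable, 60/arm (plan 0.516) | Detectable, 39/arm (plan 0.643) | Power, 60/arm (plan 80%) |
|---|---|---|---|---|---|
| 0.3 | 35% | 30% | 0.418 | 0.522 | 93% |
| 0.5 | 25% | 21% | 0.449 | 0.560 | 90% |
| 0.7 | 15% | 13% | 0.478 | 0.597 | 86% |
| 0.9 | 5% | 4% | 0.505 | 0.631 | 82% |

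Simulation of 20,000 trials per setting gave ANCOVA-to-change variance ratios of 0.661, 0.763, 0.867 and 0.956 at 60 per arm, and 0.667, 0.756, 0.865 and 0.962 at 39 per arm. At ρ = 0.99 they were 1.004 and 1.010, so the worst loss is about 1%.

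**What the plan implies about ρ.** Section 9.2 converts SD units with the cross-sectional SD: "Thus, a decrease of 0.516 SD units corresponds to a change of" −1.2384, which is −0.516 × 2.40. The SD of change is 2.40 × √(2(1−ρ)), which equals 2.40 only at ρ = 0.5. The plan does not assert that value, so it is not evidence for a 25% gain.

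**The case against.** The strongest reply is that nothing here is wrong. The endpoint is change, the interaction tests change, and the sample size rests on change, so the plan is coherent. A constrained model is then an optional refinement whose benefit depends on a correlation that the documents never give.

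For density that correlation may well be high. Section 2.3.1 reports scan reproducibility of r² = 0.997. At ρ = 0.3 the SD of individual 12-month change would be 2.40 × √1.4 = 2.84, larger than the spread between women, which is hard to square with so precise a measure. The power column also fixes the effect at 0.516 SD of change, so each row is a different raw effect. For the plan's raw target of −1.2384 with SD 2.40 and 60 per arm, planned and adjusted power (slope cost included) are 66% and 83% at ρ = 0.3, 80% and 90% at 0.5, 95% and 97% at 0.7, and above 99.9% for both at 0.9. Finally, Section 9.1 does not name a month-12 contrast. With linear time the variance cut runs from 39.6% to 5.1%, and for the average of months 6 and 12 from 46.7% to 6.7%.

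Much of this stands. The analyses are valid, the primary-endpoint gain may be small, and the gain for the stated raw target matters mainly at low or moderate ρ. It does not remove the point. Reproducibility of the scan is not stability over 12 months, and hormones, cytokines and metabolites may track less closely than density. The other readings of the time effect give slightly larger gains. The possible loss is about 1%, and only at extreme ρ.

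**Conclusion.** The concern holds as a loss of efficiency. The planned tests are valid and unbiased, and the stated power is right for them. For the month-12 contrast with complete data, the avoidable variance is (1−ρ)/2, from 35% at ρ = 0.3 to 5% at ρ = 0.9. With the planned dropout it is about 30% to 4%. This rests on equal variances at baseline and follow-up, visit fitted as a factor, and an assumed ρ. For breast density the gain is near the low end if density tracks strongly over the year. The change should be made, because adjustment costs almost nothing and is worse only above ρ of about 0.97 to 0.98.

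**What to change.** Before unblinding, prespecify one model for every mixed-model endpoint: visit as a factor, a single baseline mean common to both arms, treatment-by-visit terms at months 6 and 12, and an unstructured covariance over the three visits. Fix the covariance in advance, in place of the expected compound symmetry or selection by AIC. With complete data and visit as a factor, the planned interaction estimate does not depend on the covariance structure, but with a common baseline it does.

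For the metabolites, replace the t-test on change by ANCOVA of the post-intervention value on the baseline value and arm, and compute the q-values from those tests.

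The cost is a short SAP paragraph and revised model code. No new data are needed. The statistical price is the variance inflation from the estimated slope, about 0.9% at 60 per arm and 1.4% at 39 per arm. The constraint adds nothing for women without a baseline MRI, since they have no later MRI either.
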